10.1.2 Blood sampling time schedule

Table 10.1.2: 1 Time schedule for blood sampling during treatment schedule A, treatment with both, BI 6727 on days 1 and 15 and cytarabine on Days 1 to 10

Treatment Period	Visit	Day	CRF Time/PTM	Event	Sample No	Analysed for BI 6727	Analysed for cytarabine
Cycle 1	1	1	-0:05	PK Blood + ECG	C1 S1	X	X
			0:00 Start of admin	Drug admin			
			0:30	PK Blood	C1 S2	X	X
			1:00 Just before end of BI 6727 infusion	PK Blood + ECG	C1 S3	X	X
			1:30	PK Blood	C1 S 4	X	X
			2:00	PK Blood + ECG	C1 S5	X	X
			3:00	PK Blood	C1 S6	X	X
			4:00 ¹	PK Blood + ECG	C1 S7	X	X
			24:00	PK Blood + ECG	C1 S8	X	
	2	5	96:00	PK Blood	C1 S9	X	
3	10		216:00 Last dose of cytarabine	PK Blood	C1 S10	X	
4	15		335:55	PK Blood +	C1 S11	X	

Treatment Period	Visit	Day	CRF Time/PTM	Event	Sample No	Analysed for BI 6727	Analysed for cytarabine
				ECG			
			336:00 Start of BI 6727 infusion	Drug admin			
			336:30	PK Blood	C1 S12	X	
			337:00 Just before end of BI 6727 infusion	PK Blood + ECG	C1 S13	X	
			337:30	PK Blood	C1 S14	X	
			338:00	PK Blood + ECG	C1 S15	X	
			339:00	PK Blood	C1 S16	X	
			340:00 ¹	PK Blood + ECG	C1 S17	X	
	7	28	648:00 ²	PK Blood	C1 S18	X	
Cycle 2	1	1	-0:05	PK Blood + ECG	C2 S1	X	X
			0:00 Start of BI 6727 infusion	Drug admin			
			1:00 Just before end of BI 6727 infusion	PK Blood + ECG	C2 S2	X	X

¹ sampling between 4 and 6 hours after dose administration of BI 6727

² Sample taken any time during visit 7 at the end of cycle 1

Please note: Blood samples during and at the end of infusion have to be taken from the opposite arm than the infusion arm.

Table 10.1.2: 2

Time schedule for blood sampling during treatment schedule B, treatment with BI 6727 on days 1 and 15

Treatment Period	Visit	Day	CRF Time/PTM	Event	Sample No	Analysed for BI 6727
Cycle 1	1	1	-0:05	PK Blood + ECG	C1 S1	X
			0:00 Start of BI 6727 Infusion	Drug admin		
			0:30	PK Blood	C1 S2	X
			1:00 Just before end of BI 6727 infusion	PK Blood + ECG	C1 S3	X
			1:30	PK Blood	C1 S4	X
			2:00	PK Blood + ECG	C1 S5	X
			3:00	PK Blood	C1 S6	X
			4:00 ¹	PK Blood + ECG	C1 S7	X
		2	24:00	PK Blood + ECG	C1 S8	X
			96:00	PK Blood	C1 S9	X
			216:00	PK Blood	C1 S10	X
	4	15	335:55	PK Blood + ECG	C1 S11	X
			336:00 Start of BI 6727 Infusion	Dose admin		
			336:30	PK Blood	C1 S12	X
			337:00 Just before end of BI 6727 infusion	PK Blood + ECG	C1 S13	X
			337:30	PK	C1 S14	X

Treatment Period	Visit	Day	CRF Time/PTM	Event	Sample No	Analysed for BI 6727
				Blood		
			338:00	PK Blood + ECG	C1 S15	X
			339:00	PK Blood	C1 S16	X
			340:00 ¹	PK Blood + ECG	C1 S17	X
7	28		648:00 ²	PK Blood	C1 S18	X
Cycle 2	1	1	-0:05	PK Blood + ECG	C2 S1	X
			0:00 Start of BI 6727 infusion	Drug admin		
			1:00 Just before end of BI 6727 infusion	PK Blood + ECG	C2 S2	X

¹ Sampling between 4 and 6 hours after dose administration of BI 6727

² Sample taken any time during visit 7 at the end of cycle 1

Please note: Blood samples during and at the end of infusion have to be taken in the opposite arm of the infusion arm.

Table 10.1.2: 3

Time schedule for blood sampling during treatment schedule C, treatment with cytarabine on Days 1 to 10

Treatment Period	Visit	Day	CRF Time/PTM	Event	Sample No	Analysed for cytarabine
Cycle 1	1	1	-0:05	PK Blood	C1 S1	X
			0:00 Start of cytarabine administration.	Drug admin		
			0:30	PK Blood	C1 S2	X
			1:00	PK Blood	C1 S3	X
			1:30	PK Blood	C1 S4	X
			2:00	PK Blood	C1 S5	X
			3:00	PK Blood	C1 S6	X
			4:00 ¹	PK Blood	C1 S7	X

¹ sampling between 4 and 6 hours after dose administration of cytarabine

2. LIST OF ABBREVIATIONS

Term	Definition / description
AE	Adverse Event
ALKP	Alkaline Phosphatase
ALT	Alanine Amino Transferase
AML	Acute Myeloid Leukemia
APTT	Activated Partial Thromboplastin Time
ASR	Annual Safety Report
AST	Aspartate Amino Transferase
AUC	Area under the concentration-time curve
BI	Boehringer Ingelheim
BRPM	Blinded Report Planning Meeting
CMAX	Concentration at Maximum
CR	Complete Remission
CRi	Complete Remission With Incomplete Blood Recovery
CTCAE	Common Terminology Criteria For Adverse Events
CTP	Clinical Trial Protocol
CTR	Clinical Trial Report
eCRF	Electronic Case Report Form
DLT	Dose Limiting Toxicity
DM&SM	Data Management and Statistics Manual
DQRM	Data quality review meeting
ECG	Electrocardiogram
ECOG	Eastern Cooperative Oncology Group
EFS	Event Free Survival
EMEA	European Medicines Agency
FACS	Fluorescence Activated Cell Sorting
HGB	Hemoglobin
IB	Investigator Brochure
ICH E3	International Conference on Harmonisation - Efficacy 3
IDEA	International Document Management and Electronic Archiving
INR	International Normalized Ratio

Term	Definition / description
LD-Ara-C	Low Dose Ara-C
MedDRA	The Medical Dictionary For Regulatory Activities
MQRM	Medical Quality Review Meeting
MTD	Maximum Tolerated Dose
NC	No Change
O*C	Oracle Clinical
PD	Progressive Disease
PK	Pharmacokinetic
PR	Partial Remission
PT	Preferred Term
PV	Protocol Violation
QTc	(Frequency) Corrected QT-Time
SD	Standard Deviation
SOC	System Organ Class
TAH	Therapeutic Area Head
TCM	Trial Clinical Monitor
TMM	Team Member Medicine
TMW	Team Medical Writer
TPONT	Troponin
TSAP	Trial Statistical Analysis Plan
TSTAT	Trial Statistician
URPM	Unblinded Report Planning Meeting
WBC	White Blood Cell Count

3. INTRODUCTION

This TSAP will describe both the analyses for the final CTR as well as the analyses made for the safety update after phase I (see section [9.5](#)).

3.1 CLINICAL OBJECTIVES

See section 2.1 of the CTP.

3.2 STATISTICAL DESIGN / MODEL

The trial will be performed as an open label study. In phase I patients will be assigned to the two treatment schedules (BI 6727 monotherapy and BI 6727 in combination with LD-Ara-C, respectively). In phase II patients will be randomly allocated to one of the two different treatment schedules BI 6727 in combination with LD-Ara-C and to a monotherapy schedule with LD-Ara-C only, respectively. To determine the two separate MTDs in the phase I part, cohorts of patients will be entered sequentially into escalating dose tiers using the 3+3 design with dose de-escalation.

3.3 NULL AND ALTERNATIVE HYPOTHESES

All analyses in this study are descriptive and exploratory by nature. Any statistical tests are performed only to provide a statistical framework from which to view the results and providing aid for planning further studies. No formal statistical tests are foreseen.

3.4 STATISTICAL SOFTWARE

[REDACTED] or higher will be used for all analyses.

4. CHANGES IN THE PLANNED ANALYSIS OF THE STUDY

- An additional comparison of objective response rates based on a Bayesian approach has been added.
- Blood products uses have been added as another endpoint in order to reflect supportive care requirements.
- The definition of relapse-free survival and remission duration has been changed. The definition now includes patients who have best response of CR or CRI and not only patients with CR in order to correct a misprint in the CTP.
- Genetic groups have been defined and the analysis of overall response, event-free survival and overall survival in these subgroups has been added.

5. ENDPOINTS

5.1 PRIMARY ENDPOINTS

This study has two separate primary endpoints for the phase I part and the phase II part. The primary endpoint for the phase I part is the determination of the two separate MTDs (mono and combi) as reflected by the dose limiting toxicities (DLT) events in course 1. The primary endpoint for the phase II part is objective response.

5.1.1 Primary endpoint related to safety

The primary objective related to safety (phase I part) of this trial is to determine the MTDs of BI 6727 mono and BI 6727 in combination with LD-Ara-C. This will be done in the phase I part of the trial. Two separate MTDs for the two schedules will be determined.

Maximum tolerated dose (MTD):

The MTD for BI 6727 monotherapy is defined as the dose of BI 6727 (without LD-Ara-C), which is one dose tier below the lowest dose at which two or more out of six patients experienced DLT. The MTD for the combination schedule of BI 6727 and LD-Ara-C is defined analogously.

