4.1.3 Selection of doses in the trial

Two treatment schedules will be investigated in the phase I part of the trial to determine the MTD. All patients will receive either BI 6727 on days 1 and 15 either as monotherapy or in combination with LD-Ara-C (2 x 20 mg/d on days 1-10) in 28-day cycles. The starting dose of BI 6727 in treatment schedule A is 150 mg and corresponds to 50 % of the recommended Phase II dose of 300mg and 38% of the MTD of 400mg that has been determined in a phase I monotherapy dose escalation trial to be well tolerated.

To determine the MTD (for definition see 5.2.4), dose escalation for BI 6727 will be conducted following the “3 + 3 design with de-escalation” ([R04-0569](#)). A cohort of three patients will be treated at the starting dose level and observed until the end of the cycle. The dose level will be escalated with each new cohort until at least one out of three patients of a cohort experiences DLT (for definition see [section 5.2.3](#)). If one patient experiences a DLT, then three additional patients will be treated at the same dose level; if none of the three additional patients experiences a DLT, then the dose escalation will be continued by treating the next cohort of three patients at the next higher dose level. If at least two out of up to six patients at a dose level experience a DLT, the MTD has been exceeded and the dose will be deescalated until a dose level is reached in which at most one DLT out of six patients is observed ([R01-0028](#)). A dose step for escalation shall not exceed 50 mg/administration, a dose step for de-escalation shall not exceed 50 mg/administration.

The starting of BI 6727 for dose escalation in schedule B will be the dose determined as BI 6727 MTD in schedule A.

The dose of the trial drug on days one and fifteen will always remain the same (i.e. simultaneous and equal dose escalation for days one and fifteen). The dose of cytarabine remains always unchanged.

In case two or more cases of DLT are observed at the starting dose of 150 mg either in monotherapy or in combination with LD-Ara-C the dose BI 6727 will be deescalated to a lower dose cohort as outlined above.

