5.2.4 Maximum tolerated dose

The MTD is defined as the highest dose at which six patients have been treated and less than two patients experienced DLT within the first cycle of treatment. The MTD will be defined based on safety data from the first cycle only. However, the data from later treatment cycles will be considered for future development of BI 6727 in this indication. To determine the MTD of BI 6727 on days 1 + 15 in combination with LD Ara-C (schedule A), the dose escalation starting with 150 mg BI 6727 will be conducted following the "3 + 3 design with de-escalation" as described in [section 4.1.3](#). To determine the MTD of BI 6727 on day 1 + 15 monotherapy (schedule B), the dose escalation starting with the BI 6727 MTD determined in schedule A will be conducted following the "3 + 3 design with de-escalation" as described in [section 4.1.3](#).

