7.3.1 Primary analyses

7.3.1.1 Assessment of the MTD and derived variables for first cycle only

One primary objective for this study is the tolerability and safety of BI 6727 as monotherapy and in combination with cytarabine, respectively, as reflected by the MTD (for definition of MTD please refer to [5.2.4](#)).

In addition, to determine the MTD, an analysis on conditional probabilities for a DLT given the dose will be done, based on the logistic regression model.

For the analysis of the tolerability and safety, please refer to [section 7.3.3](#).

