7.3.4 Interim analyses

Early analyses of response to therapy will be performed before completion of recruitment in order to support internal strategic decision making and planning for future clinical trials. In order to avoid bias of these early efficacy analyses on trial conduct, the results will not be distributed to trial sites before database lock for the CTR (see [section 6.2.3.3](#)). The analyses will be performed when approximately 50% of planned patients in the phase II part of the trial have either stopped treatment or completed at least two treatment cycles. Details of the early analyses of response to therapy will be specified in the interim trial statistical analysis plan. The early efficacy analyses will be documented and archived. If considered necessary for internal strategic decision making the early efficacy analysis may be repeated once when approximately 70% of planned patients in the phase II part of the trial have either stopped treatment or completed at least two treatment cycles.

After all patients of treatment schedule A that are contained in the full analysis set (phase I) have either completed at least one course of BI 6727 in combination with cytarabine or

dropped out of the study, a safety analysis will be performed. For this purpose a database snapshot will be performed. The safety analysis will summarize results regarding safety of the patients in the phase I part and will contain the determination of the MTD as well as a recommendation for the dose of BI 6727 to be used in the phase II part of the study. The selection of the recommended dose for the phase II part will consider overall safety observed during all treatment cycles. No efficacy comparisons will be performed in this phase I safety analysis. Detailed specifications of the phase I safety analysis are provided in the TSAP. The phase I safety analysis will be documented and archived.

For other safety purposes database snapshots can be performed as deemed appropriate.

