7.6 DETERMINATION OF SAMPLE SIZE

7.6.1 Determination of the maximum tolerated dose

In oncology trials, the “standard design” is a rule-based up-and-down scheme using cohorts of three patients (e.g. 3+3 design, or the modified Fibonacci dose escalation, see Edler and Burkholder in Crowley ([R07-0220](#))). The operating characteristics of the standard design are discussed in different papers and are summarized by Storer in Crowley ([R07-0220](#)). The standard design and all other designs, that approach the MTD from below, will tend to yield a low estimate of the MTD. In addition, it is “robust”, that means that the design will determine a reasonable MTD and that escalation will be sensible, given the observed DLTs (see Potter [R07-0223](#)).

Table 7.6: 1 shows the probabilities of two or more out of six patients to be observed with DLT for some assumed probabilities of experiencing DLT in a certain dose group. There will be a probability of at least 80 % for two or more patients to exhibit DLT, if the underlying individual probability for a patient in that dose group to reach DLT is 42 % or larger.

Table 7.6: 1 Probability of observing DLT in patients experiencing dose limiting toxicity, from binomial distribution

Individual probability of observing DLT	0.40	0.42	0.45
Probability of observing DLT in two or more out of six patients	0.77	0.80	0.84

Thus, the determined MTD is defined as the highest dose of the treatment drug (BI 6727 for the two different schedules) at which no more than one out of six patients experience DLT in the first cycle.

For the planned sample size it is assumed that 5 different dosage groups are needed per treatment schedule with 2 additional dosage tiers of 3 patients (3+3 design). It is assumed that the average number of patients in a dosage group as well as in a dosage tier will be 3 (including replacement patients).

Altogether this leads to an estimated sample size of 21 patients per treatment schedule. Note that this calculation does so far not include any additional patients to be included at the presumptive MTD. Naturally, the calculated sample size of 21 patients per treatment schedule represents only a rough estimation since the number of patients needed is induced by the 3+3 design and is subject to different influencing factors.

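### Does SAP 5.1.1 leave the MTD undefined when a dose tier fails after only three patients?

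*SAP*

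**What the plan says.** Three protocol sections and one SAP section describe the MTD.

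- Protocol 5.2.4 starts from the tolerated dose: the MTD is the "highest dose at which six patients have been treated and less than two patients experienced DLT within the first cycle of treatment".
- Protocol 7.6.1 does the same in shorter form: the highest dose "at which no more than one out of six patients experience DLT in the first cycle".
- Protocol 4.1.3 gives the conduct rule: "If at least two out of up to six patients at a dose level experience a DLT, the MTD has been exceeded". De-escalation then continues until a tier shows at most one DLT in six patients. Expansion from three to six during escalation is stated only for one DLT among the first three.
- SAP 5.1.1 starts from the failing dose. The monotherapy MTD is the dose "which is one dose tier below the lowest dose at which two or more out of six patients experienced DLT", and the combination MTD is defined in the same way.

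SAP 5.1 bases the endpoint on course 1 DLTs, so the time window matches the protocol. SAP 3.2 says that "cohorts of patients will be entered sequentially into escalating dose tiers using the 3+3 design with dose de-escalation". SAP section 4 lists four changes to the planned analysis, and none concerns the MTD.

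**The concern.** SAP 5.1.1 omits two things that the protocol states. It drops the words *up to* before six when it describes the failing tier, and it sets no patient number at the declared dose. It also does not cite Protocol 5.2.4.

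Suppose a tier has DLTs in two of its first three patients and stops, and the tier below is then filled to one DLT in six. Protocol 5.2.4 names the lower tier. If the SAP's six must be six treated patients, no tier meets its failing condition and it names no dose. The rule recovers only if a lower tier later fails with six patients treated. Taken alone, the SAP could also accept a lower tier with only three patients, which Protocol 5.2.4 does not.

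The MTD is the phase I primary endpoint and informs the phase IIa dose, so a rule with no answer for an ordinary 3+3 outcome would be a real defect. The SAP does declare another redefined endpoint in section 4 (relapse-free survival and remission duration), which makes the silence here look like an oversight.

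**Working it through.** **1. The protocol's own figure.** Table 7.6: 1 gives the chance of two or more DLTs in six patients. With DLT risk p and q = 1 − p, this is 1 − q⁶ − 6pq⁵.

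- p = 0.40: 1 − 0.0467 − 0.1866 = 0.767 (table 0.77)
- p = 0.42: 1 − 0.0381 − 0.1654 = 0.797 (table 0.80)
- p = 0.45: 1 − 0.0277 − 0.1359 = 0.836 (table 0.84)

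The table reproduces. It describes the failing criterion as two or more of six, although 4.1.3 lets a tier stop at three. The protocol itself therefore uses six as shorthand alongside the fuller conduct rule.

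**2. How ordinary a three-patient stop is.** Under 4.1.3 a tier fails at three patients with probability 3p²q + p³. It fails at six with probability 3pq²(1 − q³). At p = 0.40:

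- at three: 0.288 + 0.064 = 0.352
- at six: 0.432 × 0.784 = 0.339
- share stopped at three: 0.352 / (0.352 + 0.339) = 51%

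The same formula gives 36%, 43% and 60% at p = 0.20, 0.30 and 0.50. The case cannot be dismissed as rare, so the answer depends on how the sentence reads.

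**3. What two DLTs in three patients imply.** The DLT count cannot fall as patients are added. Two or more in the first three therefore means two or more in six, whatever the next three would have shown. As a threshold, the SAP's criterion is already met when the tier stops. SAP 5.1.1 does not say that six must have been treated at the failing tier. Protocol 5.2.4 requires six only at the MTD.

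**4. The two rules on any path with a failing tier.** Call k the lowest tested tier with two or more DLTs among up to six patients.

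- Escalation stops at the first failing tier. De-escalation moves down from there until a tier has at most one DLT in six. Every tested tier from k upward has therefore failed, and none can be the MTD under Protocol 5.2.4.
- The tier next below k is where de-escalation ended. It has six patients and at most one DLT, so it is the highest dose that meets Protocol 5.2.4.
- That same tier is one below k, which is the SAP's MTD.

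The second bullet also supplies the six patients that the SAP sentence leaves unstated, because the design fills the tier before the search ends.

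**5. Numerical check.** The documents give no DLT curve, so three six-tier curves were assumed: (.05, .08, .12, .17, .25, .33), (.05, .10, .17, .25, .35, .45) and (.05, .10, .20, .40, .60, .75). Each was run 200,000 times. Some tier failed in 86.9%, 97.3% and 100.0% of runs. With six read as up to six, the SAP and protocol results agreed in all of these, including runs where both fell below the lowest modelled tier.

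With six read as a completed denominator, the SAP gave no MTD in 29.5%, 35.8% and 43.1% of runs because every failing tier had stopped at three. Where that strict reading did give an MTD, it equalled the protocol's. These three percentages depend on the assumed curves and measure only the strict reading. The agreement in step 4 does not depend on any curve.

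**The case for a change.** The best case for a change is that a primary endpoint rule should not need the reader to supply missing words, least of all when Protocol 4.1.3 writes them out. It is also fair to ask which text governs. Protocol 7.3.4 says "Detailed specifications of the phase I safety analysis are provided in the TSAP", the SAP introduction says the SAP covers the final report "as well as the analyses made for the safety update after phase I", and 5.1.1 is the only MTD definition in the SAP text available. SAP 7.7.1 and 7.7.4.2 then use the term MTD group without defining it.

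What stands is that the wordings differ and that SAP 5.1.1 has no cross-reference. The rest is weaker:

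- Protocol 7.3.1.1, which covers the primary MTD analysis, points back to 5.2.4 ("for definition of MTD please refer to"), and SAP 3.2 adopts the same design. An analyst has both in hand.
- The sponsor's clinical monitor oversees escalation steps under the protocol (4.1.4). The MTD group outputs are descriptive and take whichever dose that process produced.
- A paraphrase that yields the same dose is not a change of analysis, so section 4 need not list it. The relapse-free survival entry is different because it altered which patients are counted.
- SAP 9.5, cited for the phase I safety update, is not in the text available. It cannot be said that 5.1.1 is the SAP's last word on the matter.

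One difference remains. If escalation ended with no failing tier, SAP 5.1.1 would give no MTD, while Protocol 5.2.4 could still point to a tier that happened to hold six patients. Protocol 4.1.3 does not foresee that ending, and neither document says what would then be reported.

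**Conclusion.** No change follows. SAP 5.1.1 is a loose paraphrase of the protocol's MTD rule: a clerical shorthand that an analyst resolves from the design both documents adopt. On every path with a failing tier the two definitions name the same dose, so the effect on the reported MTD is nil and new wording would alter no result.

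This rests on two assumptions: that de-escalation under Protocol 4.1.3 is carried through to a tier with at most one DLT in six, and that a tier means a tested dose level. It does not rest on any DLT curve. The passages are reconciled by reading them together, and no view is taken on which clinical rule is right.

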5.1.2 Primary endpoint related to efficacy

The primary endpoint for efficacy (phase II part) in this study is objective response. This primary endpoint will be determined in the phase II part of the study. For the phase I part this endpoint will also be determined but will be considered as secondary only.

In order to evaluate the objective response, the investigator's assessment as given in the eCRF will be taken into account (no central review and no check vs. bone marrow measurement is planned). Both investigator assessments (clinical progression as well as response assessment) will be taken into account for the determination of objective response. In particular this means that a patient is considered as 'progressive disease' if any of the assessments indicates a progression of the disease.

No confirmation of a response / stable disease is necessary, i.e. in the following only unconfirmed responses are considered.

Evaluation of objective response:

The different categories possible for overall response (at a specific timepoint) are provided in section [9.6](#). In order to derive objective response the secondary endpoint best overall response will be derived first.

The best overall response is the best overall response recorded during the time period from the start of the treatment until end of treatment period, progression or death whichever is earlier. Possible categories for best overall response are complete remission (CR), complete remission with incomplete blood recovery (CRi), partial remission (PR), no change (NC),

progressive disease (PD) and no assessment. Patients dying before any assessment will be summarized under PD regarding best overall response.

Objective response (yes/no) is yes if the best overall response is either CR or CRI, otherwise it is no.

Objective response including PR (yes/no) is yes if the best overall response is either CR, CRI, or PR otherwise it is no.

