5.1.1.1 Definition of response

Response to treatment will be evaluated according to the following criteria (modified from the National Cancer Institute/Cancer and Leukemia Group B criteria, R06-0452):

- ! Complete remission (CR)
morphologically leukaemia free state (i.e. bone marrow with < 5% blasts by morphologic criteria and no Auer rods, no evidence of extramedullary leukaemia) and absolute neutrophil count $\geq 1,000/\mu\text{L}$ and platelets $> 100,000/\mu\text{L}$.
- ! Complete remission with incomplete blood count recovery (“incomplete” CR, CRi)
All of the above criteria for CR must be met, except that neutrophils $< 1,000/\mu\text{L}$ or platelets $< 100,000/\mu\text{L}$ in the blood.
- ! Partial remission (PR)
All of the above criteria for CR must be met, except that the bone marrow contains $\geq 5\%$ but less than 25% blasts (or $\leq 50\%$ of initial blast count), or < 5% blasts in the presence of Auer rods or abnormal morphology.
- ! No change
Patient survives ≥ 7 days following completion of initial treatment cycle with persistent leukaemia in the last peripheral blood smear or bone marrow ($>25\%$ blasts), or with persistent extramedullary disease, but without further clinical deterioration due to leukaemia or increase of blast population in the bone marrow or peripheral blood.
- ! Progressive disease (PD)
Patient survives ≥ 7 days following completion of initial treatment cycle with increase of blast population in the bone marrow or peripheral blood or aggravation or new development of extramedullary disease or further deterioration or death due to leukaemia. Patients with a global deterioration of health status requiring discontinuation of treatment without objective evidence of pd at that time should be classified as having ‘symptomatic deterioration’. Every effort should be made to document the objective pd even after discontinuation of treatment.
- ! Aplasia
Patient survives ≥ 7 days following completion of initial treatment cycle, then dies while cytopenic, with the last post-treatment bone marrow aplastic or hypoplastic (i.e. $<20\%$ cellularity) and without leukaemia blasts.
- ! Indeterminate
(a) Patient survives < 7 days after completion of initial treatment cycle; or (b) patient survives ≥ 7 days following completion of initial treatment cycle, then dies with no persistent leukaemia in the peripheral smear but no post-treatment bone marrow examination or (c) patient does not complete the first cycle
- ! Recurrence (relapse)

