after CR reappearance of leukaemic blasts in the blood or $> 5\%$ blasts in the bone marrow not attributable to any other cause.

Patients with the response status “aplasia” or “indeterminate” will be treated as non-responders for primary statistical analyses of efficacy parameters.

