7.3.1.2 Assessment of the primary efficacy endpoint and derived variables

The primary endpoint for efficacy is best objective response derived from the data of all cycles. The primary analysis will be done for all patients of the full analysis set (phase II) for all treatment schedules separately. Each patient will be assigned to one of the response categories described in [section 5.1.1.1](#).

Each patient's best response will be used as a primary measure. To describe response over time, the proportions of patients in each response category will be tabulated at specified time intervals.

The number of patients with objective response (best response is CR or CRi) will be summarised. Patients will be followed up for assessment of response and progression until they progress, receive any other anti-leukaemia therapy, die, or until the trial ends. The observed length of follow-up and the number of patients available for analysis at each time point will determine the period of time covered in tables and figures.

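### The SAP tabulates deaths before any assessment as progressive disease, although the protocol classes a death in cycle 1 as indeterminate; only the best-response tables are affected

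*SAP*

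**What the plan says.** SAP 5.1.2 derives best overall response, which it calls a secondary endpoint, and then reads objective response off it. Its category list runs from CR, CRi, PR and no change to "progressive disease (PD) and no assessment"; there is no indeterminate entry. For early deaths it adds: "Patients dying before any assessment will be summarized under PD regarding best overall response". The binary endpoint follows: "Objective response (yes/no) is yes if the best overall response is either CR or CRI, otherwise it is no".

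The protocol handles the same patients differently.

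- Section 7.3.1.2, on the primary efficacy endpoint: "Each patient will be assigned to one of the response categories described in" section 5.1.1.1.
- Section 5.1.1.1, indeterminate: one limb is survival of less than 7 days after the initial cycle; another is that the "patient does not complete the first cycle". Neither depends on the cause of death.
- Section 5.1.1.1, PD: the patient must survive at least "7 days following completion of initial treatment cycle with increase of blast population in the bone marrow or peripheral blood", or with another listed sign of progression.
- The same section says that indeterminate patients "will be treated as non-responders for primary statistical analyses of efficacy parameters".

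SAP section 4 lists changes to the planned analysis, among them a revised definition of relapse-free survival and remission duration. It does not mention early deaths.

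**The concern.** Two explicit rules give one patient two labels. A patient who dies of infection in cycle 1, with no sign of leukaemia progression and no response assessment, is indeterminate under the protocol and PD under the SAP.

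At stake is how the response distribution reads. In the PD row, early death from any cause is merged with resistant leukaemia. Protocol 1.4 notes that the two drugs have overlapping toxicities, and protocol 3.1 says the results should inform further development, so the distinction is useful to the reader. Protocol 7.3.2.1 also plans a summary of whether each death was plausibly related to progression. The same report could show a death as unrelated to progression there and as PD in the response table.

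**Working it through.** No stated figure is in dispute, so the check sets the rules side by side and then traces which outputs depend on the label.

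**Step 1: who is affected.** A cycle lasts four weeks (protocol 3.1), and the first marrow response assessment comes at its end (protocol 5.1.1; the flow charts allow it up to 3 days earlier).

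| Death without a response assessment | Protocol 5.1.1.1 | SAP 5.1.2 |
|---|---|---|
| During cycle 1 | Indeterminate (cycle not completed) | PD |
| Less than 7 days after cycle 1 | Indeterminate | PD |
| At least 7 days after cycle 1, no leukaemia in the smear, no post-treatment marrow | Indeterminate | PD |
| At least 7 days after cycle 1, due to leukaemia | Can be PD | PD |

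The rules conflict in the first three rows and need not conflict in the last.

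**Step 2: which outputs use the label.** For one arm let n be the treated patients, r those with CR or CRi, d those with PD as the protocol defines it, and k the early deaths that the SAP moves to PD.

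- Objective response is r/n under both rules. SAP section 7 bases percentages on all patients in the set, so the k patients stay in the denominator.
- The odds ratio, Fisher's test and conditional power use only r and n. So does the Bayesian posterior, beta(1+r, 1+n−r), in SAP 7.4.1.
- Response including PR is unchanged, because neither PD nor indeterminate counts.
- Event-free survival: SAP 5.2.1 uses the death date for a patient who dies without a response assessment, whatever the label. Overall survival uses the death date alone.
- The PD row is (d+k)/n under the SAP and d/n under the protocol.

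**Step 3: size per patient.** With the planned n = 43 per arm (protocol 7.6.2), each relabelled patient moves the PD row by 1/43 = 2.3 points.

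**Step 4: an illustration with invented counts.** Take 13 and 6 responders of 43, and 10 other PD patients per arm. Objective response is 13/43 = 30.2% against 6/43 = 14.0%, with Fisher's two-sided p = 0.1175, under both codings for 0, 2, 4, 6 or 8 early deaths per arm. The PD row under the protocol rule stays at 10/43 = 23.3%. Under the SAP rule it is 12/43 = 27.9% with 2 early deaths, 14/43 = 32.6% with 4, 16/43 = 37.2% with 6, and 18/43 = 41.9% with 8. This shows which quantity moves; it is not a forecast.

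**Step 5: where it would be seen.** Protocol 7.3.1.2 plans response categories for each schedule separately, and SAP 7.4 keeps the primary analysis by schedule. SAP 7.4.1 adds best-overall-response tables by genetic subgroup.

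**The case against.** The strongest reply is that little depends on this. The SAP states its convention openly, all analyses are exploratory (protocol 7.2, SAP 3.3), and no test or decision rule uses the PD row. Causes of death, overall survival and serious adverse events are reported elsewhere, so early deaths are not hidden. All of this stands, and it is why the point is minor. It does not remove the conflict with protocol 7.3.1.2 or the missing entry in SAP section 4.

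A second reply concerns scope, and it also stands. The SAP sentence refers to any assessment, and SAP 5.1.2 draws on both clinical-progression and response assessments. Blood and clinical disease assessments are scheduled from visit 1. Read literally, a patient who dies late in cycle 1 has already been assessed and falls outside the sentence, so the number affected could be close to zero. SAP 5.2.1 refers to patients without any response assessment, which supports the wider reading but does not settle it.

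A third reply is that counting early death as PD is conservative. It is not so for the primary endpoint, where the result is no under either label.

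A reader might also infer that the protocol's aplasia category has no place in the SAP list. The documents do not establish that. Aplasia describes a cytopenic patient who dies "with the last post-treatment bone marrow aplastic or hypoplastic" and without blasts; as written, such a marrow can also meet the CRi criteria. SAP 9.6, which holds the time-point categories, is not in the available text.

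**Conclusion.** The inconsistency is real and minor. A death in cycle 1 without leukaemia progression and before any assessment is indeterminate under the protocol and PD under the SAP, and the departure is not recorded. The effect is confined to the best-overall-response tables, at 2.3 points per relabelled patient in an arm of 43.

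Two stronger readings are not supported. One is that the primary result is biased: for these patients objective response and its comparisons, event-free survival and overall survival are identical under both rules. The other is that the PD comparison between arms is distorted in a known direction or by a known amount: the documents give no early-death rate in either arm.

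The conclusion rests on reading the protocol's 7-day survival condition as governing the whole PD definition. If death due to leukaemia were read as a separate route to PD, a cycle 1 death from another cause would still not qualify. How many patients are involved depends on the unresolved meaning of any assessment.

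**What to change.** In SAP 5.1.2, before database lock:

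- change the condition to death before any response assessment, which matches SAP 5.2.1;
- classify these deaths by protocol 5.1.1.1, as indeterminate where that definition applies, in place of the blanket PD rule;
- add an indeterminate row to the best-overall-response tables, and show deaths before the first response assessment by arm;
- keep objective response as no for these patients, as protocol 5.1.1.1 requires;
- record any departure from the protocol categories that remains in SAP section 4.

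The cost is a few words of SAP text and one extra table row. The sample size, the primary comparison, event-free survival and overall survival are unchanged.
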